Acute chest-pain syndromes are the second most common reason for emergency department (ED) visits with more than 6.5 million such visits occurring annually in the United States.

Although acute coronary syndrome (ACS) is ultimately diagnosed in only 5.1% of patients who present with chest pain, many of these patients are admitted to hospitals, at an estimated cost of over \$3 billion annually (1,2). In addition, patients with chest pain return for additional care within one week at a rate of up to 10% (3). This places additional strain on EDs and hospitals.

Recent updates to the guidelines for acute chest pain management in the emergency department setting place CCTA as a 1A “for intermediate-risk patients with acute chest pain and no known CAD”. Further, FFR_{CT} was given 2aB-NR as an add-on diagnostic test “for intermediate-risk patients with acute chest pain and no known CAD, with a coronary artery stenosis of 40% to 90% in a proximal or middle coronary artery on CCTA. FFR_{CT} can be useful for the diagnosis of vessel-specific ischemia and to guide decision-making regarding the use of coronary revascularization” (1).

In the ED, coronary computed tomography angiography (CCTA) is a beneficial noninvasive technique for use in patients with acute chest pain, due to its high accuracy for detection of coronary artery disease (CAD); however, an increase in CCTA can often be followed by an increase in invasive coronary angiography (ICA) (4). With increasing health care expenditures, there is ever-expanding focus on appropriate resource utilization. To that end, the historically high rates of nonobstructive disease at the time of ICA are being increasingly scrutinized.

HeartFlow, Inc. (‘HeartFlow’) provides a non-invasive method to determine the hemodynamic significance of CAD (FFR_{CT}) from subject-specific CCTA data using computational fluid dynamics under simulated maximal coronary hyperemic conditions (5). Results from two prospective trials suggest that FFR_{CT} accurately predicts the hemodynamic significance of coronary lesions when compared to invasively measured FFR (6,7). FFR_{CT} is available in Japan, in many European countries (CE mark 2011), in Canada, and in the U.S. (De Novo 510K clearance 2014).

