The ROMICAT II trial showed that CCTA in the ED reduces cost and length of stay when compared to standard of care (8). Additional studies such as the PLATFORM (Prospective Longitudinal Trial of FFR_{CT}: Outcome and Resource Impacts Study) and CONSERVE (Coronary Computed Tomographic Angiography for Selective Cardiac Catheterization) trials have highlighted the potential for CCTA and FFR_{CT} to help inform ICA referral in an effective and safe fashion. Work by Chinnaiyan, et al done in the ED, went on to show that FFR_{CT} leads to cost savings with no increase in MACE, and a negative FFR_{CT} (suggestive of a non-hemodynamically significant lesion) is particularly useful in patients with >50% stenosis showing significantly lower revascularizations and costs (9).

The ADVANCE-ED study is a prospective multi-center study in which clinically stable, symptomatic patients who present to the ED or observation unit with suspected CAD will have at least one >40% lesion and no lesions >90% in a major vessel, confirmed by CCTA. All enrolling sites will have CCTA incorporated into their standard evaluation of chest pain in the ED. Non-control sites have CCTA and FFR_{CT} analysis incorporated into their standard evaluation of chest pain in the ED/observation unit. For non-control sites, the treating healthcare provider will be asked to provide a management plan prior to the results of the FFR_{CT} being available. Subjects will be followed up at 30 days, and data will be collected for

any additional testing, office visits, hospital admissions, procedures, and outcomes.

II. STUDY OBJECTIVE

Primary Objective

The primary objective of the ADVANCE-ED study is to compare decision plans prior to FFR_{CT} with the actual decision made after FFR_{CT}.

Secondary Objectives

The secondary objectives are to evaluate utility, clinical outcomes, and resource utilization when FFR_{CT} analysis is incorporated in the emergency department (ED) or observation unit for clinically stable, symptomatic patients with suspected CAD to further inform patients, health care providers, and other stakeholders about which technologies are most effective and efficient in the diagnosis and management of ACS and CAD.

III. STUDY ENDPOINTS

A. Primary Endpoint

The primary endpoint of ADVANCE-ED is the reclassification rate between the coronary management plan based on the review of the CCTA compared to the actual management.

B. Secondary Endpoints

The secondary endpoints include:

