- Cost utility analysis to include length of stay, secondary coronary testing, and invasive coronary procedures
- Major Adverse Coronary Event (MACE) rates at day 30
- Rate of invasive catheterization without obstructive disease at day 30
- Time to diagnosis
- Time to discharge

IV. STUDY DESIGN

All non-invasive and invasive data collected will be obtained from clinical practices that are standard clinical care. All details about cardiovascular testing and treatment (planned and actual) will be recorded at baseline.

IV. A. Location and Number of Subjects

Approximately 500 subjects will be enrolled from approximately 20 experienced clinical research sites across the US.

All enrolling sites will have CCTA incorporated into their standard evaluation of chest pain in the ED/observation unit. Approximately half of the sites will be FFR_{CT} sites who will have CCTA and FFR_{CT} analysis incorporated into their standard evaluation of chest pain in the ER/observation unit. Sites who have CCTA but not FFR_{CT} incorporated into the ED/observation unit will be control sites.

If FFR_{CT} is implemented at a control site during the enrollment period, site can request to switch over to the non-control arm once FFR_{CT} has been successfully implemented. This switch must be reviewed and approved by the HeartFlow Clinical Research team.

No site may enroll more than 75 (15%) subjects in the trial.

IV. B. Patient Population

The population for this study will be clinically stable, symptomatic patients who present to the ED or observation unit with suspected CAD and while in the ED or observation unit, have a CCTA performed which shows at least one >40% lesion and no lesions >90% in a major epicardial vessel, a successfully processed FFR_{CT} (if applicable), and no history of coronary artery disease.

IV. C. General Inclusion and Exclusion Criteria

Inclusion Criteria (all must be present):

1. Age ≥18 years
2. Clinically stable, symptomatic patients who present to ED/observation unit with suspected CAD
3. CCTA shows at least one >40% lesion and no lesions >90% in at least one major epicardial vessel
4. FFR_{CT} processed successfully (if applicable)
5. EKG with no acute ischemic changes
6. Willing to comply with all aspects of the protocol, including adherence to follow up visit
7. Agrees to be included in the study
8. Able to provide written informed consent

Exclusion criteria (all must be absent):

1. CCTA showing no >40% lesion in a major epicardial vessel

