2. CCTA showing a lesion >90% in a major epicardial vessel
3. CCTA showing other incidental, non-cardiac findings requiring admission, i.e., pneumonia or pulmonary embolism
4. Uninterpretable CCTA which is not of diagnostic quality
5. CABG or PCI prior to CCTA acquisition
6. Left main lesion >50%
7. Confirmed of acute coronary syndrome (acute myocardial infarction or unstable angina)
8. Known complex congenital heart disease or any history of coronary artery disease
9. Patients with tachycardia or significant arrhythmia which cannot be adequately controlled with medications to allow CTA
10. Any active, serious, life-threatening disease with a life expectancy of less than 2 months
11. Inability to comply with follow-up requirements
12. Currently enrolled in another study utilizing FFR_{CT} or in an investigational trial that involves a non-approved cardiac drug or device
13. Persons under the protection of justice, guardianship, or curatorship

V. STUDY WORKFLOW

The workflow for ADVANCE-ED is described in the following sections.

V. A. Study/Site Selection

HeartFlow will identify and qualify the clinical research sites for ADVANCE-ED. Participating sites will be screened for:

- CCTA acquisition practices conforming to SCCT guidelines
- Adequate resources and past clinical research experience
- HeartFlow's ED Connect in active use and an ED/observation unit pathway including CCTA and FFR_{CT} in place for non-control sites
- An ED/observation unit pathway including CCTA for control sites

V. B. Subject Selection

Institutional review board approval will be obtained at all participating sites prior to screening patients. All patients who meet all inclusion criteria and do not meet any exclusion criteria, and are able and willing to participate, are candidates for ADVANCE-ED. All patients providing written informed consent and meeting all selection criteria will be enrolled into the study.

V. C. Screening Period

1. All subjects must fulfill all study inclusion criteria and no study exclusion criteria.
2. Each subject will undergo the following assessments to be documented in the appropriate electronic case report form (eCRF) upon enrollment:
 - a. Collection of demographic information
 - b. A summary of the subject's relevant medical history and cardiovascular risk factors
 - c. Information about the subject's CCTA results
 - d. Information about the subject's FFR_{CT} results (non-control sites)

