 - e. Decision plan prior to FFR_{CT} results (non-control sites)

V. D. Enrollment

All subjects must provide written informed consent prior to enrollment. A notation will be made in the subject's medical chart, if required by the institution, and in the study records that he/she is participating in the study, has had his/her questions answered, has read, signed, and dated the Informed Consent Form (ICF), and been given a copy of the ICF.

All subjects who meet eligibility requirements will be asked to participate. Subjects will be considered enrolled in the study after the following criteria have been met:

1. Informed consent form has been signed and subject has been provided a copy.
2. All inclusion criteria and no exclusion criteria have been met.

V. E. Follow up

A 30 day (± 7 days) follow up phone call with the subject following baseline visit will be done as a part of this study. Data collected will include:

- Current cardiac health status
- Any additional hospital admissions

- Any additional ED/observation unit visits
- Any cardiac procedures/tests
- MACE

Sites will also be asked to provide billing information (UB-04 preferred) from baseline to day 30. Reports and images for CCTA, FFR_{CT} (if applicable), ICA, and other cardiac tests will be uploaded to the eCRF.

VI. STUDY DURATION

The anticipated enrollment duration of ADVANCE-ED will be approximately 18 months. A 30 day follow up phone call is planned for this study.

VI.A. Rules for Subject Withdrawal

Each subject is free to withdraw from the study at any time. No additional data will be collected after a subject informs the Investigator that they want to withdraw.

VI. B. Rules for Terminating the Study

There are no formal termination criteria for this study. The sponsor reserves the right to terminate ADVANCE-ED at any time. Investigators have the responsibility to comply with all applicable regulatory guidelines and regulations. Specific reasons which may cause the sponsor, the Institutional Review Board, or local regulatory authorities to terminate a center include, but are not limited to:

- 1) Failure of the investigator to comply with investigator agreement, protocol, guidelines, and/or regulations.
- 2) Serious protocol violations.
- 3) Submission of knowingly false information from the research facility to the sponsor, clinical monitor, or other party involved in the study.

VI. C. Rules for switching from Control arm

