Sites who do not have FFR_{CT} incorporated into the ED/observation unit will be control sites. If FFR_{CT} is implemented at a control site during the enrollment period, site can request to switch over to the non-control arm once FFR_{CT} has been successfully implemented. This switch must be reviewed and approved by the HeartFlow Clinical Research team.

VI.D. SAFETY ASSESSMENT

Patients will undergo a clinically indicated CCTA and any other invasive physiological measurements, which do not require additional radiation, extra contrast, or additional procedure time for this study/protocol. All procedures performed will be per standard clinical care, and data obtained will be documented as per standard of clinical care. Therefore, there will be no additional clinical risks for subjects who participate. MACE will be collected at day 30. MACE is defined as the composite rate of all cause death, non-fatal myocardial infarction (MI) and unplanned hospitalization for acute coronary syndrome (ACS) leading to urgent revascularization.

VI.E. RATIONALE AND ETHICAL CONSIDERATIONS

This prospective, multi-center study is being conducted to provide real world evidence potentially in support of including FFR_{CT} in an ED pathway.

The potential risks to subjects participating in this study include potential breach of confidentiality. Data transmitted to HeartFlow will not contain any PHI identifiers and will be coded with a unique identifier for each subject. All applicable study data will be transferred to HeartFlow and core laboratories in a secure manner and in accordance with all applicable regulations.

Anticipated benefits

There are no specific benefits to subjects participating in the study. There may be some benefit to other patients who undergo FFR_{CT}-guided management in the future.

Anticipated risks

ADVANCE-ED is a prospective study which collects data from clinically-indicated CCTA imaging and other procedures. These procedures will have been planned as part of routine clinical practice; therefore, no additional clinical risks are related to participating in the study.

IX. STATISTICAL CONSIDERATIONS

IX. A. General Considerations

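### The MACE definition counts a non-MI ACS readmission only if it leads to urgent revascularization, a decision FFRCT may inform in one arm only, so arms with equal readmission rates could show different MACE counts, in either direction

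*Combined protocol and SAP*

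**What the plan says.** Section III.B lists "Major Adverse Coronary Event (MACE) rates at day 30" as a secondary endpoint. Section VI.D defines MACE as a composite of death from any cause, non-fatal MI and "unplanned hospitalization for acute coronary syndrome (ACS) leading to urgent revascularization". It is the only outcome named in that safety section.

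Section I gives FFRCT a role in the same kind of decision. The guideline statement cited there says it can be used "to guide decision-making regarding the use of coronary revascularization". The earlier ED study cited there found a negative FFRCT particularly useful, with "patients with >50% stenosis showing significantly lower revascularizations and costs".

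FFRCT results are recorded at non-control sites only (V.C). The control arm, about 250 subjects like the FFRCT arm, serves the secondary endpoints alone (IX.D). There is no events committee (XI.E). The 30-day call collects "Any additional hospital admissions", as well as ED visits, cardiac procedures and MACE, and sites are asked for billing to day 30 (V.E).

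**The concern.** Whether an unstable-angina readmission becomes a MACE event depends on a treatment choice, not only on what happened to the patient. That choice belongs to a class that FFRCT is meant to inform, and only one arm has the result. If the result carries over to the later admission, the composite partly measures how the test changes treatment.

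A subject discharged on a negative FFRCT who returns with unstable angina and is managed without urgent revascularization adds nothing to MACE. No other clinical endpoint in section III counts that admission. It is also the kind of event a reader would want to see when judging whether deferral on a negative FFRCT was safe. After a positive FFRCT, the same definition could add events in the FFRCT arm that would not have been counted in a comparable control subject.

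**Working it through.** **The plan's own figure.** The only sample-size figure is 208 subjects for an exact 95% interval of width 0.14 at a reclassification proportion of 0.5 (IX.D). The Clopper-Pearson interval at n = 208 is 0.4301 to 0.5699, width 0.1399. At n = 207 the width is 0.1402, so 208 is the smallest adequate n and the figure reproduces. It concerns the primary endpoint. The plan gives no rate, test or power for MACE.

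**What the definition drops.** Exclusion criterion 7 (IV.C) treats ACS as acute MI or unstable angina. I assume the same meaning in VI.D. Fatal cases and MIs enter MACE through their own components. What is lost is the non-MI ACS readmission without urgent revascularization.

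**Model.** Expected MACE events per arm = 250 × (d + r × c), where
- 250 is the arm size (IX.D);
- d is the death or MI rate, assumed 1% in both arms;
- r is the non-MI ACS readmission rate, assumed equal in the arms and varied from 1% to 10%;
- c is the share of those readmissions leading to urgent revascularization, assumed and allowed to differ by arm.

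The gap between arms is 250 × r × (c control − c FFRCT). Example at r = 5%, shares 50% and 25%: control 250 × (0.01 + 0.05 × 0.50) = 8.75; FFRCT 250 × (0.01 + 0.05 × 0.25) = 5.63; ratio 0.64.

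Cells show control vs FFRCT events, with the FFRCT-to-control ratio in brackets:

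| r | c 50% vs 25% | c 70% vs 50% | c 25% vs 50% |
|---|---|---|---|
| 1% | 3.75 vs 3.13 (0.83) | 4.25 vs 3.75 (0.88) | 3.13 vs 3.75 (1.20) |
| 2% | 5.0 vs 3.75 (0.75) | 6.0 vs 5.0 (0.83) | 3.75 vs 5.0 (1.33) |
| 5% | 8.75 vs 5.63 (0.64) | 11.25 vs 8.75 (0.78) | 5.63 vs 8.75 (1.56) |
| 10% | 15.0 vs 8.75 (0.58) | 20.0 vs 15.0 (0.75) | 8.75 vs 15.0 (1.71) |

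The absolute gap runs from 0.5 event (4.25 − 3.75) to 6.25 events (15.0 − 8.75). In the first column, the chance that a two-sided 5% comparison of the arms would reach significance through this artefact alone is about 4% to 26%.

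**Direction.** The FFRCT-arm share is a mixture over results. If half of those readmitted had a negative FFRCT with share 40% and half a positive one with share 80%, then c = 0.5 × 40% + 0.5 × 80% = 60%. Against a control share of 60% the gap is zero. The documents give neither the mix of results nor the shares.

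**Broader count.** Counting every unplanned ACS hospitalization gives 250 × (d + r) in each arm: 5, 7.5, 15 and 27.5 events at r = 1%, 2%, 5% and 10%. The ratio is 1.00 whatever the revascularization shares. This follows from r being set equal, and it assumes the ACS label is applied alike in both arms.

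**The case against.** The strongest reply has four parts.

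*The link to a later admission is inferred.* Section I describes FFRCT informing revascularization and reports fewer procedures after a negative result. It does not address urgent revascularization at an unplanned admission up to a month later, when new symptoms, ECG and troponin may decide. This stands: the influence is plausible but not documented.

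*The bias need not favour FFRCT.* A reader might infer that the dropped readmissions must fall mainly in the FFRCT arm and make the product look safer. For example, 10 readmissions per arm (4% of 250) with assumed shares of 60% and 40% give 6 versus 4 counted, which could be read as a spurious one-third reduction. The documents do not support that reading. The cited reduction concerns negative results only, positive results can act the other way, and all three inputs are assumed. Moreover, 6 versus 4 in arms of 250 has a Fisher p of 0.75, and two arms each expecting 6 Poisson events differ by 2 or more about 66% of the time with no bias at all.

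*No confirmatory MACE claim is planned.* Section IX.A reserves intervals and tests for the primary and selected efficacy endpoints. The arms are also formed by site practice, and control sites may switch (VI.C), which limits any between-arm reading in any case. This lowers the weight of the point, but it does not supply the missing count.

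*The condition hardens a soft label.* Without adjudication, requiring a procedure gives a verifiable criterion, and the ACS label itself may be affected by knowledge of FFRCT. That is a fair reason to keep the stated MACE. It is not a reason to leave the other admissions untabulated. Data listings (IX.A) are not a planned comparison by arm.

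**Conclusion.** The concern holds as a limited measurement problem. Equal rates of non-MI ACS readmission could give different MACE counts by arm, because one component depends on a treatment decision that FFRCT may inform in one arm only. Neither size nor sign can be estimated from the documents. Under the assumed rates it is a few events per 250-subject arm, which is small in absolute terms but can be a large part of a composite this rare.

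The conclusion rests on two inferences: that clinicians at readmission know the index FFRCT result, and that it affects their choice. A reader might also infer that MACE misses every ACS readmission without revascularization. It does not, since non-fatal MI and death count regardless. The primary endpoint and the sample size are unaffected. This is an inexpensive improvement to a secondary safety endpoint, not a defect that invalidates it.

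**What to change.** Keep the MACE of section VI.D as stated. In the SAP, before outcome data are examined:

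1. Prespecify a supportive MACE whose third component is unplanned hospitalization for ACS after index discharge, regardless of revascularization.
2. Tabulate ACS hospitalizations with and without urgent revascularization by arm and, in the FFRCT arm, by FFRCT result.
3. State that any between-arm MACE comparison will be interpreted in light of both versions.

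The cost is SAP wording and one table. Admissions, procedures and billing to day 30 are already collected (V.E), so no subjects, visits or changes to care are added. The drawback is that the broader component relies on site-reported ACS labels. These are softer than a procedure and may also be influenced by knowledge of FFRCT, so the supportive version removes the dependence on revascularization but not every effect of an unblinded test. The report should say so.

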Hypothesis	The primary hypothesis of this study is that using HeartFlow's FFR _{CT} analysis as part of the treatment pathway for clinically stable, symptomatic patients with suspected CAD in the ED/observation unit can result in a more streamlined diagnostic pathway and therefore provide cost-effective clinical care for patients.
Population	The population for this study will be clinically stable, symptomatic patients who present to the ED or observation unit with suspected CAD and no history of coronary artery disease, and who while in the ED or observation unit have a CCTA performed which shows at least one $\geq 40\%$ lesion and no lesions $> 90\%$ in a major epicardial vessel, and a successfully processed FFR _{CT} (if applicable).

Study Design and Methods	
This is a prospective multi-center study. All clinically stable, symptomatic patients who present to the ED or observation unit with suspected CAD and who have at least one $\geq 40\%$ lesion and no lesions $< 90\%$ lesion in a major vessel, confirmed by CCTA, are eligible for enrollment once their CCTA has been completed and FFR_{CT} (if applicable) has been ordered. All enrolling sites will have CCTA incorporated into their standard evaluation of chest pain in the ED/observation unit. Non-control sites will have CCTA and FFR_{CT} analysis incorporated into their standard evaluation of chest pain in the ED/observation unit.
 
All sites will provide demographics, medical history, CCTA images, FFR_{CT} (for non-control sites), the decision plan post CCTA and pre FFR_{CT} (for non-control sites), length of stay for patients in the ED/observation unit/hospital, billing reports (UB-04 preferred), 30-day clinical outcomes, and any other hospital or office visits, imaging, and/or procedural data completed prior to the follow-up 30-day visit.
 
Sites which do not have FFR_{CT} incorporated into the ED/observation unit will be control sites. If FFR_{CT} is implemented at a control site during the enrollment period, the site can request to switch over to the non-control arm once FFR_{CT} has been successfully implemented in the ED/observation unit at that site. This switch must be reviewed and approved by the HeartFlow Clinical Research team.

Primary Endpoint	The primary endpoint of ADVANCE-ED is the reclassification rate between the coronary management plan based on the review of the CCTA compared to the actual management.

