Descriptive statistical methods will be used to summarize the data from this study, with confidence intervals and hypothesis testing performed for the primary and other selected efficacy endpoints. Unless stated otherwise, the term “descriptive statistics” refers to number of events (n), mean, median, standard deviation (SD), standard error, (SE) minimum, maximum, and coefficient of variation (CV) for continuous data and frequencies and percentages for categorical data.

All data collected during the study will be included in data listings.

Unless specified otherwise, all statistical testing will be two-sided and will be performed using an overall significance (alpha) level of 0.05.

All statistical analyses will be conducted with the SAS® System, version 9.4 or higher.

A statistical analysis plan (SAP) will describe the methods of data collection, validation, analysis, and reporting. The sections below provide a brief overview of statistical consideration for the study.

IX. B. Subject Characteristics

Subject accountability will be described, including number of subjects enrolled, number of subjects included in the analysis, and reasons for any subjects discontinued from the study or was not included in the analysis. Demographic information will be summarized using descriptive statistics. Sex and medical histories will be summarized by counts and percentages.

IX. C. Endpoint Analysis

The null hypothesis for the primary endpoint is that the reclassification rate between the coronary management plan based on the review of the CCTA compared to the actual

management after FFR_{CT} is obtained is zero. A one-sample exact binomial test will be used to analyze the primary endpoint. In addition, the proportion with reclassification along with the 95% exact confidence interval will be produced.

IX. D. Sample Size

FFR_{CT} arm: Approximately 250 subjects may be enrolled into this study. A sample size of 208 produces a two-sided 95% exact confidence interval with a width equal to 0.14 when the proportion with reclassification is 0.5.

Control arm: The control arm will contribute only to secondary endpoints and is therefore not included in the powering of the primary endpoint but will be the same size as the FFR_{CT} arm and will include approximately 250 subjects.

IX. E. Analysis Populations

All subjects who meet the study criteria, and who sign the written informed consent, are enrolled in the study.

X. DATA HANDLING AND QUALITY ASSURANCE

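### The primary test uses a null reclassification rate of exactly zero, so a single reclassified patient rejects it and the p-value says nothing about whether the rate is meaningful

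*Combined protocol and SAP*

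**What the plan says.** Section IX.C (Endpoint Analysis) opens with "The null hypothesis for the primary endpoint is that the reclassification rate between the coronary management plan" formed after CCTA and what was actually done. It ends that sentence with the null value and then names the test: "management after FFR_{CT} is obtained is zero. A one-sample exact binomial test will be used to analyze the primary endpoint". As an addition to the test, "the proportion with reclassification along with the 95% exact confidence interval will be produced".

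Section IX.A (General Considerations) applies by default: "all statistical testing will be two-sided and will be performed using an overall significance (alpha) level of 0.05". It also says that hypothesis testing is done for the primary endpoint, and it leaves methodological detail to a SAP. Nothing in the text available replaces the zero null.

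Section IX.D (Sample Size) does not use this test. It is a precision calculation: "A sample size of 208 produces a two-sided 95% exact confidence interval with a width equal to 0.14" at an assumed reclassification proportion of 0.5. About 250 subjects are planned for the FFRCT arm. The control arm is assigned to secondary endpoints only.

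**The concern.** A hypothesis test is useful when its null is a value that the data could plausibly be consistent with, so that rejection rules something out. A null of exactly zero for a proportion is refuted by one event, with no sampling error involved. The test then reports only whether the count is above zero, which anyone can see from the count.

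What is at stake is how the primary result reads. A trivial rate and a large one would both be reported as p = 0. A reader who takes the primary p-value as evidence that FFRCT changes management to a worthwhile extent would be misled. No minimum meaningful rate, performance goal or reference rate appears anywhere in the documents to set against it.

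**Working it through.** **Inputs.** From IX.C: null rate p0 = 0, one-sample exact binomial test. From IX.A: two-sided, alpha 0.05. From IX.D: n = 208, interval width 0.14, planning rate 0.5, about 250 subjects planned. The small true rates below (0.5% to 5%) are assumptions chosen to show the behaviour of the test; the documents do not give them.

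**Step 1: the plan's own figure.** The exact (Clopper-Pearson) interval at x = n/2 has limits given by the 0.025 quantile of Beta(x, n − x + 1) and the 0.975 quantile of Beta(x + 1, n − x).
- n = 208, x = 104: 0.4301 to 0.5699, width 0.1399.
- n = 206, x = 103: width 0.1405.

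So 208 reproduces as the smallest n with width at most 0.14. The sample size stands.

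**Step 2: the p-value under p0 = 0.** P(X = 0) = (1 − 0)^n = 1, so P(X ≥ 1) = 0. For n = 208 and n = 250:
- x = 0 gives p = 1.
- x = 1, 2, 5 or 10 each gives p = 0, one-sided or two-sided.

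The rejection rule is x ≥ 1. Its type I error is exactly 0, and it is the same rule at any alpha between 0 and 1.

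**Step 3: the smallest significant result.** 1/208 = 0.48%. The exact lower limit is 1 − 0.975^(1/208) = 0.00012 and the upper limit is 0.0265, so the CI is 0.01% to 2.65%. The exact lower limit is above zero whenever x ≥ 1, so the planned interval already contains everything the test reports.

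**Step 4: probability of rejection.** P(X ≥ 1) = 1 − (1 − p)^n.

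| True rate p | n = 208 | n = 250 |
|---|---|---|
| 0.5% | 1 − 0.995^208 = 0.647 | 0.714 |
| 1% | 1 − 0.99^208 = 0.876 | 0.919 |
| 2% | 1 − 0.98^208 = 0.985 | 0.994 |
| 5% | 0.99998 | >0.9999 |
| 50% (planning value) | practically 1 | practically 1 |

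**Step 5: what a non-zero null would ask for.** The thresholds here are illustrative assumptions. Exact test, upper tail at most 0.025, n = 208:

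| p0 | Smallest rejecting count | Type I error | Power at 0.5 |
|---|---|---|---|
| 0.10 | 31 (14.9%) | 0.016 | >0.999 |
| 0.20 | 54 (26.0%) | 0.022 | >0.999 |
| 0.30 | 77 (37.0%) | 0.018 | >0.999 |
| 0.40 | 98 (47.1%) | 0.022 | 0.816 |

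With n = 250 and p0 = 0.40, the smallest rejecting count is 116 (46.4%) and power is 0.885. If the planning rate of 0.5 is near the truth, the planned size would support a test against a real threshold over much of this range.

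**The case against.** The best defence is that the informative analysis is already planned. The proportion and its exact CI will be reported, the study is sized on that interval, and no success criterion or gatekeeping hangs on the p-value. A result of 1 in 208 would appear next to an interval ending at 2.65%, and few readers would be impressed by it. All of this stands. It confines the defect to the test and makes the repair easy, but it does not give the test a purpose.

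Some stronger readings are tempting, and the documents do not support them.

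- *The endpoint will be significant whatever FFRCT does.* Not strictly. At a true rate of 0.5% the test rejects 65% of the time, and at 1% it rejects 88% of the time. Rejection is practically certain at higher rates, including the planning value.
- *The null is known to be false because plans and delivered care always differ.* The documents give no background rate of plan change. What can be said is that a planning value of 0.5 shows the sponsor expects the rate to be far from zero.
- *A two-sided test is impossible at zero.* It can be computed. The lower side is empty, so two-sidedness is redundant.
- *The test fails because the hypothesis is directional.* The Study Synopsis does hypothesise that FFRCT "can result in a more streamlined diagnostic pathway and therefore provide cost-effective clinical care for patients". The primary objective, however, is a non-directional comparison of plan with decision, and counting any change matches it. Cost and timing are covered by secondary endpoints. Any gap between hypothesis and endpoint is a separate matter, and changing the null would not close it.

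**Conclusion.** The primary hypothesis test in Section IX.C is wrong as written. Its p-value can take only the values 0 and 1, its type I error is 0 whatever alpha is declared, and one reclassified patient in 208 meets it. It therefore provides no evidence that the reclassification rate is large enough to matter.

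The degeneracy follows exactly from p0 = 0 and needs no assumption. The rejection probabilities rest on independent subjects and on the assumed true rates shown. The conclusion also assumes that no separate SAP text changes the null; none was available to check. A reader might infer that the sample size or the estimate is compromised too, but neither is: 208 reproduces, and the exact interval remains valid and informative.

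**What to change.** 1. **Delete the test against zero.** Make the proportion reclassified with its exact 95% CI the primary analysis. This agrees with the precision-based sizing in Section IX.D and leaves n unchanged. It costs protocol and SAP wording only.
2. **If a p-value is wanted,** prespecify a non-zero threshold and justify it. The sponsor must supply the figure and its basis.
3. **As a supportive analysis,** report escalation and de-escalation separately, using prespecified management categories. The documents define none, so this needs definitions and possibly eCRF fields.
4. **Optionally, as a secondary analysis,** add a McNemar test of planned versus actual invasive angiography in FFRCT-arm subjects. It tests net change, so equal movement in both directions would give a null result despite a high reclassification rate. It cannot replace the primary estimate. Having no comparator, it also does not separate an FFRCT effect from ordinary plan change.

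A comparison of plan-to-actual change between the FFRCT and control arms is not recommended on the planned data. Section V.C lists the decision plan for non-control sites only. The general remark in Section IV about recording planned and actual care does not clearly extend it to controls.

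The price of the change is the loss of a near-certain significant p-value. No information is lost.
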